#### **7.2.2 Subgroup Analysis**

The AR-V7-negative and positive cohorts at baseline will be compared for all analysis. All subgroup analysis will be based on the full analysis and per protocol sets. If there are very few AR-V7 patients recruited, outcomes will be only described.

For time to event endpoints (PFS, OS, time to first symptomatic SSE, TTP-AF, and TTP-PSA), we will use the Kaplan-Meier method and Log-Rank test. For binary outcomes we will use Chi-squared or Fisher's exact tests.

We also analyze PFS and OS with multivariable Cox proportional hazards models including AR-V7 status, CTCs levels and other relevant baseline covariates, including PSA level, number of prior hormonal treatments, the presence or absence of visceral metastases, the Eastern Cooperative Oncology Group (ECOG) score, and prior use of abiraterone acetate or enzalutamide. All tests were two-sided, and P values of 0.05 or less were considered to indicate statistical significance. We will examine the residuals to assess model assumptions and only first-order interactions will be evaluated. We will calculate relative risk (RR) and HR with corresponding 95% CI to compare dichotomous and time to event variables, respectively.

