Four slides will be thawed from each patient, then cells will be fixed with 2% paraformaldehyde, permeabilized with cold methanol, and non-specific binding sites will be blocked with goat serum. Slides will be subsequently incubated with monoclonal anti-pan CK antibody (Sigma) and CD45-Alexa 647 (Serotec) for 40 minutes at 37°C. After PBS washes, slides will be incubated with Alexa Fluor 555 goat anti-mouse antibody (Invitrogen) for 20 minutes at 37°C. Cells will be counterstained with DAPI for 10 minutes and mounted with an aqueous mounting media.

Detection of AR-V7 in CTCs

mRNA expression analyses will be performed using the ProstateCancerDetect kit with multiplexed reverse-transcription polymerase-chain-reaction (qRT-PCR) primers to detect the presence of CTCs, and custom primers designed to detect the full-length-AR (AR-FL) and AR AR-V7. The relative AR-V7 transcript abundance will be determined by calculating the ratio of AR-V7 to AR-FL.

Details will be provided in the study laboratory manual. All samples will be labelled with patient study number, date and time of collection.

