### 5.2 Secondary objective(s) and secondary endpoints

#### **Secondary objectives:**

- Safety profile.
- To determine the association between AR-V7 status (positive vs. negative) and rPFS.
- To establish the relationship between CTCs number with radium-223 efficacy.

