### **8.5 Handling of missing data**

For time-to-event endpoints, patients without a date of disease progression will be analyzed as censored observations on the date of last tumor assessment. If no post-baseline tumor assessment is available, patients will be censored at the date of first treatment + 1 day. Data for patients with an event (progression) who missed two or more scheduled assessments immediately prior to the event will be censored at the last tumor assessment prior to the missed visits.

For OS, patients who are not reported as having died will be analyzed as censored observations on the date they were last known to be alive. If no post-baseline data are available, OS will be censored at the date of treatment + 1 day.

EudraCT number: 2016-001888-36

For objective response and clinical benefit, patients without any post-baseline assessment will be considered non-responders.

For patients with AR-V7 status not available at baseline, we will assume the AR-V7 status provided at end of treatment or progression, whichever occurs first. Patients with AR-V7 status not available in the study will be considered as AR-V7 negative.

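### AR-V7 is read in circulating tumour cells, but the SAP has no group for samples without them, so the unadjusted AR-V7 comparisons can partly reflect CTC presence.

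*SAP*

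**What the plan says.** The assay section of Protocol Appendix 3 is headed "Detection of AR-V7 in CTCs". It states: "mRNA expression analyses will be performed using the ProstateCancerDetect kit with multiplexed reverse-transcription polymerase-chain-reaction (qRT-PCR) primers to detect the presence of CTCs", together with custom primers for full-length AR and AR-V7. The read-out is a ratio: "The relative AR-V7 transcript abundance will be determined by calculating the ratio of AR-V7 to AR-FL". The appendix gives no positivity cut-off and no category for a sample without CTCs, and leaves details to a laboratory manual. CTCs are also counted by a separate imaging method (HD-CTC).

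The SAP secondary objective is "To determine the association between AR-V7 status (positive vs. negative) and rPFS". SAP 7.2.2 says "The AR-V7-negative and positive cohorts at baseline will be compared for all analysis" and "All subgroup analysis will be based on the full analysis and per protocol sets". For time-to-event endpoints, "we will use the Kaplan-Meier method and Log-Rank test"; binary outcomes get chi-squared or Fisher tests. The same section also plans a multivariable Cox model for PFS and OS that includes AR-V7 status and CTC levels.

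For missing status, SAP 8.5 first uses the result at end of treatment or progression, whichever comes first. If there is none, "Patients with AR-V7 status not available in the study will be considered as AR-V7 negative". The per-protocol set (SAP 6) instead excludes patients without AR-V7 status.

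**The concern.** A sample with no tumour cells carries no tumour transcript, so it cannot give a positive AR-V7 result. Such a patient can be positive only through a later sample. The positive cohort therefore consists of patients who had CTCs in the sample that classified them. The negative cohort mixes patients whose CTCs lacked AR-V7 with patients in whom tumour AR-V7 was never observed.

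The plan lists the relationship between CTC number and radium-223 efficacy as a secondary objective and puts CTC levels in its Cox model, so it regards CTCs as possibly prognostic. If patients without CTCs do better, AR-V7-positive patients will look worse even when AR-V7 has no effect. That would wrongly contradict the rationale in Protocol 1.4 and the equal-efficacy hypothesis in Protocol 8.2.

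The same gap affects the McNemar analysis of AR-V7 evolution: a patient who is positive at baseline and has no CTCs later could be counted as an AR-V7 reversal.

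**Working it through.** **1. The plan's own figure.** Inputs from Protocol 8.2: median PFS 3 versus 6.3 months, one-sided alpha 0.05, power 80%, 23 months' accrual plus 11 months' follow-up, 25% AR-V7-positive. The test is the exponential maximum-likelihood test in SAP 7.1.1.
- Events needed: (1.645 + 0.842)² / [ln(6.3/3)]² = 6.183 / 0.5505 = 11.23.
- With λ = ln 2 / 6.3 = 0.110 per month, P(event) = 1 − (e^(−11λ) − e^(−34λ)) / (23λ) = 1 − (0.298 − 0.024) / 2.53 = 0.892.
- Patients: 11.23 / 0.892 = 12.6, so 13 positives, and 13 / 0.25 = 52. The stated 13 + 39 reproduces.

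**2. Where a CTC-absent baseline sample goes.**

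| Reading of the sample | Full analysis set | Per-protocol set |
|---|---|---|
| AR-V7 not detected | Negative | Negative |
| Not available, later status exists | Later status, positive or negative | Later status |
| Not available, no later status | Negative | Excluded |

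In the full analysis set, every route leads to the negative cohort except a later positive sample.

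**3. Illustration of size.** The documents give neither the CTC-free share nor its prognostic effect, so both are assumed. Set-up: no AR-V7 effect; 13 positives, all with CTCs, against 39 negatives, of whom 8, 12, 16 or 20 are CTC-free; exponential PFS with median 6.3 months when CTCs are present; hazard divided by h when they are absent; uniform censoring at 11-34 months; two-sided 5% log-rank test; 6,000 trials per cell.

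| CTC-free among the 39 | h = 1 | h = 2 | h = 3 |
|---|---|---|---|
| 8 (about 20%) | 6% | 8% | 12% |
| 12 (about 30%) | 6% | 11% | 17% |
| 16 (about 40%) | 6% | 15% | 26% |
| 20 (about 50%) | 6% | 20% | 35% |

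A repeat run gave 36% in the last cell, which is within simulation error. The apparent AR-V7 hazard ratio is about 1.3 to 1.8 for shares of 30-50%. Restricted to CTC-present patients, rejection stays at about 5-6.5%.

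A second set of assumptions used a median of 5 months with CTCs, 20-50% of all 52 CTC-free, and a median 1.5-3 times longer without CTCs. It gave apparent hazard ratios of 1.14-2.10 and rejection in 8-58%. With CTC presence added to a Cox model, the hazard ratio was 0.96-1.04 and rejection 4-6%.

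**4. Capacity of the planned Cox model.** Expected PFS events: 52 × 0.892 = 46.4. SAP 7.2.2 names seven covariates (AR-V7 status, CTC levels, PSA, number of prior hormonal treatments, visceral metastases, ECOG, prior abiraterone or enzalutamide): 46.4 / 7 = 6.6 events each.

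**5. Price of restriction.** Power = Φ(√(D·p·(1−p)) × ln 2 − 1.96), where D = 0.892n and p = 13/n, at a true hazard ratio of 2.
- 13 v 39: D = 46.4, power 53%.
- 13 v 29 (10 of 52 CTC-free): D = 37.4, power 50%.
- 13 v 21 (18 of 52): D = 30.3, power 46%.
- 13 v 13 (26 of 52): D = 23.2, power 39%.

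**The case against.** A reader might infer that every patient without CTCs is put in the negative group and that every positive patient had CTCs at baseline. The documents do not support either statement. Classification of a CTC-absent sample is not defined in them and may be in the laboratory manual. SAP 8.5 looks to a later sample first, so a patient without CTCs at baseline can become positive; the simulation, which gives all 13 positives CTCs, simplifies this. The per-protocol set drops patients who never have a status. Nor does Appendix 3 say that the assay tests for CTCs before testing for AR-V7; it lists the primers together.

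A reader might also infer that the AR-V7 question has no adjusted analysis. It has one for PFS and OS, and SAP 7.2.2 does not rank it below the log-rank test. With CTC presence coded explicitly, such a model removes the distortion in the illustration. What remains is that the coding of CTC levels is not given and the model is heavily loaded. Time to first symptomatic skeletal event, time to PSA progression, time to alkaline phosphatase progression and the binary outcomes have no adjustment.

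The modified full analysis set does not help: it requires a CTC determination, which could be zero, and serves the CTC and molecular analyses. The SAP also says that outcomes will only be described if very few AR-V7 patients are recruited. That would remove the tests but leave the Kaplan-Meier curves mixed in the same way.

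**Conclusion.** The point holds in limited form. The documents leave the status of CTC-absent samples undefined, and in the full analysis set most routes place these patients in the negative comparator. The unadjusted AR-V7 comparisons can therefore reflect CTC presence. The Cox model is a partial remedy for two endpoints.

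The size cannot be found from the documents. The 8-36% rejection range rests wholly on an assumed CTC-free share of 20-50% of the negatives and an assumed hazard ratio of 2-3. At the mild end (20%, hazard ratio 2) it is 8% against about 6% with no CTC effect. This is a secondary comparison with about 53% power at a hazard ratio of 2, and the trial's declared success rests on the total sample, which is unaffected. The change is still worth making because it uses samples already planned.

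**What to change.** In SAP 7.2.1, 7.2.2 and 8.5:
- Define three baseline groups: no CTCs detected; CTC-present and AR-V7-negative; CTC-present and AR-V7-positive. State that CTC presence comes from the RT-PCR assay that yields the AR-V7 result, or name the HD-CTC count if that is used; the two may disagree.
- Report the no-CTC group separately, and do not count unavailable status as negative.
- Base the AR-V7 contrast for every endpoint on CTC-present patients or on an analysis adjusted for CTC presence. Either is acceptable; adjustment keeps all patients.
- Code CTC presence explicitly in the Cox model.
- Keep the pooled positive-versus-negative comparison as a labelled sensitivity analysis.
- In the McNemar analysis of AR-V7 evolution, use patients with CTCs at both time points.

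The cost is SAP wording and one grouping variable, with no new samples or patients. If restriction is chosen, the comparator shrinks, with the loss of power shown in step 5 of the working.

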### 7.3 Safety analysis

All safety data will be evaluated at the first 34 months period of the study. Additionally, bone lesions will be evaluated at the 2-years safety extension after the end of the treatment. Analysis of safety-related data will consider:

- The degree of exposure (dose, duration and number of patients) will be assessed to determine the degree to which study safety can be assessed. These results will be summarized with descriptive statistics (n, NA, mean, standard deviation, median and range).
- Concomitant medications will be coded to the appropriate Anatomical-Therapeutic-Chemical (ATC) code indicating 1st to 4th levels. The results will be showed by frequency tables (frequency counts and percentage).
- For AEs, and serious adverse events (SAEs) will be assessed to determine the safety. Severity, causality, relationship to study drug, body system, action taken, and outcome will be reported.  
Adverse events will be classified into standardized medical terminology from the verbatim description (investigator term) using the Medical Dictionary for Regulatory Activities (MedDRA). Adverse events will be presented by preferred term (PT) and by system organ class (SOC). They will be analyzed using frequency tables.
- Deaths and study discontinuation for each study group will be described and assessed.

## 7.4 Demographic and baseline characteristics

Demographic and other baseline characteristics will be summarized and listed for the full analysis set. For continuous demographic/baseline variables, results will be summarized and presented as n, number of not available data (NA), mean, standard deviation, median, first and third quartiles and minimum and maximum values. For categorical variables, the number, frequency counts and percentage of subjects will be used.

Demographic and baseline characteristics are:

- Age (at the IC signature)
- Race
- Medical history
  - Diagnosis of adenocarcinoma, metastases and previous invasive cancer and other clinically significant events
  - Previous treatment for mCRPC coded according to ATC code, considering 1st to 4th levels.
  - Any other prior medications (in the 28 days prior to screening visit)
- Baseline signs/symptoms
- Physical examination and ECOG status
- Vital Signs
- Hematology and Coagulation
- PSA, testosterone determination and Biochemistry
- Brief pain inventory (short form)
- HRQoL questionnaire (FACT-P)
- AR-V7 mutational status and CTC count
- Radiological Tumor Assessment

### 7.4.1 Summary for full analysis test and overall

A baseline global table will be generated, showing the following demographic and baseline characteristics for the full analysis test and overall. This table will be used to present in a possible article.

- Age at informed consent signature, both as a continuous variable, and categorized ( $\geq 75$  years vs.  $< 75$  years).
- Prior use of Docetaxel for mCPRC
- Prior use of other anti-androgens for mCPRC
- Number of prior hormonal therapy lines for mCPRC before last abiraterone/enzalutamide treatment, categorized (0, 1,  $\geq 2$ )

EudraCT number: 2016-001888-36

- Duration of abiraterone/enzalutamide treatment (weeks)
- Use of bisphosphonates/other bone targeted therapy
- ECOG performance status
- Extent of disease (bone lesions), categorized (<6 metastases, 6-20 metastases, >20 metastases)
- Lymph node involvement
- Hemoglobin at baseline
- Albumin at baseline
- Alkaline phosphatase at baseline
- LDH at baseline
- ALT at baseline
- PSA at baseline
- AR-V7 status at baseline
- Pain severity score at baseline
- Pain interference score at baseline
- Ongoing androgen deprivation with luteinizing releasing hormone (LHRH) analogue therapy
- Bilateral orchiectomy
- External beam radiation therapy within 12 weeks before study screening

A by-subject listing of all demographic and other baseline characteristics will be provided for all patients treated.

## 7.5 ***Transformation of expected variables***

- The time to progression is defined as the difference between start of drug (C1D1) and the progression date or death (whichever occurs first) or the last radiological assessment documented.
- The time to death is defined as the difference between the time from inclusion and death.
- The time to first SSE is defined as the difference between start of drug and the first symptomatic skeletal symptom.

EudraCT number: 2016-001888-36

## 7.6 *Interim analysis protocol*

Before extension amendment, no interim analysis was planned, but an interim analysis was performed to provide results for a congress abstract.

After extension amendment, an interim efficacy analysis is planned to be performed when all patients have progressive disease.

## 8. Statistical Methods

### 8.1 *Data Quality Assurance*

All tables, figures and data listings to be included in the report will be independently checked for consistency, integrity and in accordance with standard EXPERIOR procedures. These checks will be done or coordinated within the Statistical Programming and Biostatistics department of EXPERIOR by the respective Primary Coordinator. All tables, figures and data listings provided by EXPERIOR will be also checked by MedSIR for consistency and integrity.

### 8.2 *General Methodology*

Definition of baseline: For each safety or efficacy parameter, the last valid assessment made before first study drug administration will be used as the baseline for all analyses of that safety or efficacy parameter unless otherwise specified.

Continuous data will be summarized in terms of the number of observations, mean, standard deviation (STD), median, minimum, maximum, first and third quartiles and NA (not available), unless otherwise stated. Where data are collected over time, both the observed data and change from baseline will be summarized at each time point.

The minimum and maximum will be reported to the same number of decimal places as the raw data recorded in the database. The mean, median and first and third quartiles will be reported to one more decimal place than the raw data recorded in the database. The STD will be reported to two more decimal places than the raw data recorded in the database. In general, the maximum number of decimal places reported shall be four for any summary statistic.

Categorical data will be summarized in terms of the number of subjects providing data at the relevant time point (n), frequency counts and percentages. Changes from baseline in categorical data will be summarized using shift tables where appropriate.

Percentages will be presented to one decimal place. A percentage of 100% will be reported as 100%. Percentages will not be presented for zero counts. Unless otherwise EudraCT number: 2016-001888-36

stated, percentages will be calculated using n as the denominator; for frequency tables not assessed by time point the number of patients considered for every analysis set will be used as denominator. If sample sizes are small, the data displays will show the percentages, but any textual report (e.g. clinical study report) will describe frequencies only.

P-values greater than or equal to 0.001, in general, will be presented to three decimal places. However, if a p-value is only presented to four decimal places it will not be rounded again but will be presented to four decimal places. P-values less than 0.0001 will be presented as “<0.0001”.

Confidence intervals will be presented to one more decimal place than the raw data. A two-sided significance level of 5% will be used for confidence intervals.

Statistical programming and analyses as well as all report outputs will be performed/produced using R software® version 3.3 or superior in a secure and validated environment. All report outputs will be provided to the Sponsor in a single Microsoft Word document.

### **8.3 Subject Disposition**

Descriptive statistics will be provided for the following:

- Overall number of subjects in the screening population, number of screening failures, and the number of patients enrolled.
- Number and percentage of subjects in the full analysis set.
- Listing of subjects excluded along with reason for exclusion.
- Listing of protocol deviations.
- Study termination:
  - Number and percentage of subjects who completed the study.
  - Frequency of premature termination reasons.
  - Listing of all dropouts along with reason for termination, drug exposure and time of termination.

No statistical tests are planned for these data.

### **8.4 Safety**

All safety tables will list or summarize subjects of full analysis set. Safety assessments will be subjected to clinical review and summarized by appropriate descriptive statistics.

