## **6. Analysis sets**

### Full analysis set

All patients that accomplish selection criteria and receive at least one dose of study medication.

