### Safety set

The safety set includes patients who receive at least one dose of study medication.

The primary analysis of efficacy will be performed in the full analysis and per protocol sets in all patients. Secondary and subgroup analysis of efficacy will be also performed in the full analysis and per protocol sets all patients and two study cohorts (AR-V7-negative and positive). Analysis of CTC will be performed in modified full analysis set in both cohorts and all study patients. Safety analyses will be performed in the safety set in both cohorts and all study patients.

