### **6.1 Protocol Deviations**

Protocol deviations will be recorded in the EXPERIOR database. A by-patient listing of protocol deviations and a by-patient listing of inclusion and exclusion criteria not met will be provided.

Major protocol deviations are defined as those deviations from the protocol likely to have an impact on the perceived efficacy and/or safety of study treatment.

To determine the per protocol set, all protocol deviations will be reviewed prior to database lock to determine which ones should be classified as major deviations. Patients with major protocol deviations will be excluded from the per protocol set.

Major protocol deviations may be discussed in the data review meeting. Criteria for determining full analysis set would be established by the Steering Committee (SC) before the statistical analysis begins.

Major protocol deviations and any action to be taken regarding the exclusion of subjects or affected data from specific analyses are defined below.

A summary of the number and percentage of subjects with a major protocol deviation by type of deviation will be provided. Also, a by-subject listing of major and minor protocol deviations will be provided.

Description	Category	Grade*	Rationale	Comments
Adult < 18 years	Inclusion/Exclusion criteria	Major	Safety	Automatic check
Informed consent form not signed	Inclusion/Exclusion criteria	Major	GCP breach	Automatic check. Patient data could not be used for efficacy assessment
Patient has not histologically confirmed adenocarcinoma of the prostate without neuroendocrine differentiation or small cell features	Inclusion/Exclusion criteria	Major	Efficacy	Manual Review
Patient has not bone metastases due to the prostate cancer and presence of visceral metastases	Inclusion/Exclusion criteria	Major	Efficacy	Manual Review
Serum testosterone of > 1.7 nmol/L (or > 50 ng/dL) at screening	Inclusion/Exclusion criteria	Major	Efficacy Safety	Automatic check
<24 weeks of treatment with abiraterone acetate or enzalutamide within its approved label indication and discontinuation <4 weeks prior to start of study drug at day 1	Inclusion/Exclusion criteria	Major	Efficacy Safety	Manual Review

EudraCT number: 2016-001888-36

Castration-naïve patients treated >six cycles with docetaxel	Inclusion/Exclusion criteria	Major	Efficacy	Manual Review

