Subject has received investigational therapy within 28 days or 5 half lives, whichever is longer, prior to start of study drug at day 1.	Inclusion/Exclusion criteria	Major	Efficacy Safety	Manual review
Absolute neutrophil count < 1,500/ $\mu$ L, at screening	Inclusion/Exclusion criteria	Case by case	Efficacy Safety	Automatic check
Platelet count < 100,000/ $\mu$ L, and hemoglobin < 6.25 mmol/L (or < 10 g/dL) at screening	Inclusion/Exclusion criteria	Major	Efficacy Safety	If clinically relevant** Automatic check
Subject has received growth factors or blood transfusions within seven days of the hematologic laboratory values obtained at screening	Inclusion/Exclusion criteria	Major	Efficacy Safety	Manual review
Subject has total bilirubin > 1.5 times the upper limit of normal (ULN) at screening, except for subjects with documented Gilbert's syndrome.	Inclusion/Exclusion criteria	Case by case	Efficacy Safety	Automatic check and Manual review
Subject has creatinine > 2.5 mg/dL at screening.	Inclusion/Exclusion criteria	Case by case	Efficacy Safety	Automatic check
Subject has albumin $\leq$ 30 g/L (or $\leq$ 3.0 g/dL) at screening.	Inclusion/Exclusion criteria	Case by case	Efficacy Safety	Automatic check
IMP not administered but screening completed	Inclusion	Major	Efficacy	Study discontinuation prior to treatment start

EudraCT number: 2016-001888-36

Hypersensitivity to IMP	Investigational Medicinal Product	Major	Efficacy Safety	Major if dose not administered completely
IMP overdose	Investigational Medicinal Product	Major	Efficacy Safety	
IMP underdose	Investigational Medicinal Product	Major	Efficacy Safety	
IMP administration dosing/Schedule/delays	Investigational Medicinal Product	On case by case	Efficacy Safety	If administered dose is systematically deviating from expected dose and delays not as described in protocol
IMP toxicity	Investigational Medicinal Product	On a case by case	Safety	If toxicity has not managed appropriately Listing with AE's grade 3/4 with action = none before the EOT date
Post-baseline tumor assessment not done	Study procedure	Major	Efficacy Safety	Major if no post baseline assessment done or if first post-baseline assessment is not at least after 8 weeks of treatment start.
Post-baseline tumor assessments out of the window	Study procedure	Minor	Efficacy	If done more than every 12 weeks +7 days. Major if only post-baseline assessment is not at least after 8 weeks of treatment start.

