No baseline tumor assessment	Inclusion and Exclusion criteria/ Study procedure	Major	Efficacy	If not baseline values any post-baseline data indicating presence of new bone lesions/visceral lesions could be evaluated as evidence of PD Flag if baseline data (CT and bone scans) are >28 days before day 1 cycle 1.

No post-baseline data indicating presence of ≥ 2 new bone lesions or progression as per RECIST 1.1	Study procedure	Major	Efficacy	No evidence of Radiological PD for patients not discontinued due to increased PSA, symptoms or clinical deterioration.
Visits out of window	Study procedure	Minor	Safety	If not performed every 28 days +7 days until EOT; if not performed every 3 months after EOT or if EOS not performed within 3 months after progression, lost to FUP.
Local laboratory tests out of window	Study procedure	Major	Safety	If tests scheduled for day 1 of all cycles (including screening) not performed within 72 hours prior to the dose
Screening assessments out of window	Study procedure	Case by case	Safety	If done >28 days before day 1 cycle 1. Not applicable to local lab tests.
Assessments not done during treatment period (lab value, HRQoL..)	Study procedure	Case by case	Safety	Not applicable to Radiological Assessments. Flag if systematically not done.
Blood sample for translational study not obtained or obtained at incorrect timepoint	Study procedure	Case by case	Efficacy	Depending on which sample is not collected.
Blood sample for translational study obtained out of window at screening	Study procedure	Case by case	Efficacy	Sample not obtained within 72 hours prior to the first dose
Adequate follow-up	Study procedure	Major	Efficacy	If no post-treatment evaluation according to protocol
Prohibited medication was taken	Concomitant medication	Major	Efficacy	If any therapies intended for the treatment of cancer prior to EoT (Cytotoxic chemotherapy, other systemic radioisotopes,

EudraCT number: 2016-001888-36

				radiotherapy, abiraterone acetate, enzalutamide or any antiandrogen)
Prohibited medication was taken	Concomitant medication	On a case by case	Efficacy Safety	If another investigational drug prior to EoT
Subject not withdrawn as per protocol	Administrative and Other	Major	GCP	If data is obtained after withdrawal

\* Major protocol deviation excludes from the full analysis set

\*\* Identification of clinically relevant conditions from the Medical History

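### SAP section 6 puts safety analyses on all dosed patients, but SAP 8.4 puts the safety tables on the full analysis set, which excludes dosed patients who fail selection criteria

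*SAP*

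**What the plan says.** SAP section 6 defines a separate population for safety: "The safety set includes patients who receive at least one dose of study medication". It then assigns the work to that population: "Safety analyses will be performed in the safety set in both cohorts and all study patients".

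SAP 8.4 opens with a different instruction: "All safety tables will list or summarize subjects of full analysis set". Section 8.4.1 bases exposure on the full analysis set. Section 8.4.3 names it for adverse events, SAEs, deaths and discontinuations, and 8.4.4, 8.4.5 and 8.4.6 name it for laboratory values, vital signs and physical examination. Section 8.4.2 (concomitant medications) names no set and so falls under the opening sentence of 8.4. The safety set is not mentioned anywhere in section 8, and the disposition summary in 8.3 counts only the full analysis set.

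Section 6 defines the full analysis set as "All patients that accomplish selection criteria and receive at least one dose of study medication".

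On major deviations, the SAP gives two rules. The text of 6.1 says "Patients with major protocol deviations will be excluded from the per protocol set". The footnote to the deviation table in the same section says "Major protocol deviation excludes from the full analysis set".

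Protocol 8.3.3 proposes the full analysis set for both efficacy and safety and defines no separate safety set.

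**The concern.** The SAP gives two populations for the same outputs. A programmer working from section 8, where the tables are specified, would produce every safety output on the full analysis set. A dosed patient outside that set would then contribute neither events nor exposure to the summaries, although section 6 says that patient belongs in them. Safety is a listed secondary objective, and the usual basis for describing it is everyone who received the drug.

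The size of the omission depends on which patients the full analysis set excludes. That is where the deviation-table footnote matters, because it may enlarge the excluded group well beyond ineligible patients.

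**Working it through.** The plan states no figure to reproduce. The check compares the definitions and then works out what one exclusion amounts to.

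**Step 1: do the two sets differ?** Yes. Both require at least one dose. The full analysis set adds the selection criteria; the safety set does not. On the definitions alone, the dosed patients who are in the safety set but not in the full analysis set are those who failed a selection criterion.

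**Step 2: does a major deviation also remove a dosed patient from the full analysis set?** The SAP is divided.

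- For removal: only the footnote to the table in 6.1.
- Against removal: the full analysis set definition in section 6 has no deviation filter. The per protocol definition in section 6 is the one that requires no major deviations. The text of 6.1 ties major deviations to the per protocol set. Section 8.4.1 restates the full analysis set as eligible and dosed, and nothing more.
- Unresolved: 6.1 also says the Steering Committee will set criteria for the full analysis set before analysis.

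Two further features suggest that the footnote is a slip for the per protocol set. First, SAP 7.1.1 makes the full analysis set primary and the per protocol set supportive; if both dropped every major deviation, the distinction would nearly disappear. Second, the table grades the absence of any post-baseline tumor assessment as major. Yet SAP 8.5 has a censoring rule for exactly those patients, and Appendix I Table 1 counts a death before the first assessment as an event. Under the footnote, those rules would have little or nothing to act on.

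**Step 3: who would be lost if the footnote were followed?** Rows graded major in 6.1 include:

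- overdose and underdose of study drug, both without qualifier;
- hypersensitivity, with the comment "Major if dose not administered completely";
- prohibited anticancer therapy, with the comment "If any therapies intended for the treatment of cancer prior to EoT" (use of another investigational drug is graded case by case);
- no post-baseline tumor assessment, which would cover a patient who died before the first scan.

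**Step 4: size per exclusion.** Planned enrolment is 52 (SAP 4.7). Assuming all 52 are dosed, one exclusion removes 1/52 = 1.9% of the safety population.

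**Step 5: effect on a reported rate, as illustration only.** Assume 52 dosed patients, 10 with a given serious event, and k excluded. Neither the 10 nor k comes from the documents.

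- Safety set: 10/52 = 19.2%.
- All excluded patients had the event, (10 − k)/(52 − k): k = 2 gives 8/50 = 16.0%; k = 3 gives 7/49 = 14.3%; k = 5 gives 5/47 = 10.6%.
- No excluded patient had the event, 10/(52 − k): k = 3 gives 10/49 = 20.4%.

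The rate can move either way, depending on who is excluded.

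**The case against.** The strongest reply has four parts.

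1. Section 6 already assigns safety to the safety set, so the plan is contradictory rather than committed to omitting dosed patients. This stands, and the point is framed that way. It does not remove the need for a correction, because the sections that specify the tables all name the other set.

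2. Protocol 8.3.3 uses the full analysis set for safety, so SAP 8.4 follows the protocol. This is true, and it means the protocol sentence needs aligning as well. It does not explain why the SAP defines a safety set, assigns safety to it, and then does not use it.

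3. Excluded patients do not vanish from the record. SAP 8.3 lists excluded subjects with reasons, protocol deviations, and dropouts with their exposure. Protocol 6.9 puts medication errors on the adverse event page, and Protocol 7.2 requires SAEs to be reported within 24 hours. This limits the harm, but listings and expedited reports do not restore events or denominators to the summary tables.

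4. Safety here is secondary and descriptive, and the primary rPFS test does not depend on which set the safety tables use. This also stands.

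A reader might infer that the plan definitely removes patients with overdose, hypersensitivity or prohibited therapy from the adverse event tables. The documents do not support that as a settled fact: it requires the footnote to override section 6, the text of 6.1 and 8.4.1, and it requires 8.4 to override section 6. For hypersensitivity, the dose must also have been incomplete.

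**Conclusion.** The contradiction is real and is wrong as written. If section 8 is followed, dosed patients who fail selection criteria are missing from the adverse event, SAE, death, laboratory and exposure summaries. That conclusion needs only the section 6 definitions and 8.4. The wider loss, of dosed patients with major deviations, holds only if the 6.1 footnote is followed.

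Each exclusion removes 1.9% of the safety population, assuming 52 dosed patients. The total cannot be stated, because the documents give no expected number of exclusions.

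A reader might also infer that the excluded patients are those most likely to have safety events, so that the tables would understate risk. No figure in the documents gives event rates by eligibility or deviation status, and it is not evident for underdosed patients or for most eligibility failures. The direction of any bias is therefore open. The case for correction is that the safety summaries should cover every dosed patient, as section 6 intends.

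**What to change.** - In SAP 8.4, 8.4.1 and 8.4.3 to 8.4.6, replace the full analysis set by the safety set. In 8.4.1, also drop the selection-criteria condition. Section 8.4.2 then follows from 8.4.
- In SAP 8.3, add the number and percentage of patients in the safety set.
- Correct the footnote to the deviation table in SAP 6.1 so that a major deviation excludes from the per protocol set, in line with the text of 6.1 and the definitions in section 6.
- Align Protocol 8.3.3 so that safety is analysed in all patients with at least one dose.

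The cost is text: SAP edits, plus a protocol change through the amendment or administrative letter route in Protocol 12.2. No new data or additional patients are needed. The edits should be made before it is known which patients the full analysis set would exclude, so that the choice of population cannot be seen as depending on their outcomes.
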